8.5.4. Prompt Reporting of Serious Adverse Events and Other Events

SAEs, pregnancies, and liver function abnormalities meeting pre-defined criteria will be reported promptly by the investigator to the medical monitor as described in Table 4 once the investigator determines that the event meets the protocol definition for that event. Any seizure or suspected seizure should be reported in an expedited manner, as noted in Table 4.

Criteria for liver chemistry stopping and follow-up criteria are in Section 7.1.1.

Table 4 Reporting of Serious Adverse Events and Other Events

Type of Event	Initial Reports		Follow-up Information on a Previous Report	
	Time Frame	Documents	Time Frame	Documents
All SAEs	24 hours	“SAE” data collection tool	24 hours	Updated “SAE” data collection tool
Cardiovascular (CV) or death event	Initial and follow-up reports to be completed when the cardiovascular event or death is reported ^a	“CV events” and/or “death” data collection tool(s) if applicable	Initial and follow-up reports to be completed when the cardiovascular event or death is reported ^a	Updated “CV events” and/or “death” data collection tool(s) if applicable
Pregnancy	24 hours	“Pregnancy Notification Form”	Within 24 hours of investigator awareness of pregnancy outcome	“Pregnancy Follow-up Form” and SAE if required
Seizure or suspected seizure	24 hours	eCRF	24 hours	eCRF
Suspected ABC HSR in participants receiving Oral standard of care (SOC) during the Long-Term Follow-Up Phase ^b	1 week	ABC HSR eCRF	1 week	Updated ABC HSR eCRF
ALT \geq 3 \times ULN and bilirubin \geq 2 \times ULN (>35% direct) (or ALT \geq 3 \times ULN)	24 hours ^c	“SAE” data collection tool. “Liver Event eCRF” and “Liver Imaging” and/or “Liver Biopsy” eCRFs, if applicable	24 hours	Updated “SAE” data collection tool/“Liver Event” documents

Type of Event	Initial Reports		Follow-up Information on a Previous Report	
	Time Frame	Documents	Time Frame	Documents
ALT ≥ 5 × ULN that persists ≥ 2 weeks	24 hours ^c	Liver Event eCRF ^d	24 hours	Updated Liver Event eCRF ^d
ALT ≥ 8 × ULN	24 hours ^c	Liver Event eCRF ^d	24 hours	Updated Liver Event eCRF ^d
ALT ≥ 3 × ULN (if baseline ALT is < ULN) or ALT ≥ 3 fold increase from baseline value with appearance or worsening of symptoms of hepatitis or hypersensitivity	24 hours ^c	Liver Event eCRF ^d	24 hours	Updated Liver Event eCRF ^d

- Additional details and time frames for reporting supplementary information for cardiovascular and death events are provided in Section 8.5.7 and Section 8.5.8, respectively.
- ABC HSR eCRF only required if event meets one of the ICH E2A definitions of seriousness.
- GSK must be contacted at onset of liver chemistry elevations to discuss participant safety.
- Liver event documents (i.e., "Liver Event eCRF" and updates, "Liver Imaging eCRF" and/or "Liver Biopsy eCRF", as applicable) should be completed as soon as possible.

SAE reporting to GSK via electronic data collection tool

- Primary mechanism for reporting SAEs to GSK will be the electronic data collection tool.
- If the electronic system is unavailable for greater than 24 hours, the site will use the paper SAE data collection tool and fax it to the Medical Monitor.
- Site will enter the serious adverse event data into the electronic system as soon as it becomes available.
- After the study is completed at a given site, the electronic data collection tool (e.g., InForm system) will be taken off-line to prevent the entry of new data or changes to existing data.
- If a site receives a report of a new SAE from a study participant or receives updated data on a previously reported SAE after the electronic data collection tool has been taken off-line, the site can report this information on a paper SAE form or to the Medical Monitor by telephone.
- Contacts for SAE receipt can be found at the beginning of this protocol on the Sponsor/Medical Monitor Contact Information page.
- The investigator will be required to confirm review of the SAE causality by ticking the 'reviewed' box at the bottom of the eCRF page within 72 hours of submission of the SAE.

The method of recording, evaluating, and follow-up of AEs and SAEs plus procedures for completing and transmitting SAE reports to the medical monitor are provided in the SPM. Procedures for post study AEs/SAEs are provided in the SPM. Primary and

secondary Medical Monitor/SAE contact information is provided on the Medical Monitor/Sponsor Information Page of the current protocol.

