8.5.1. Time Period and Frequency for Collecting AE and SAE Information

- Any SAEs assessed as related to study participation (e.g., protocol-mandated procedures, invasive tests, or change in existing therapy) or related to a GSK product will be recorded from the time a participant consents to participate in the study up to and including any follow-up contact.
- All SAEs will be recorded and reported to the sponsor or designee immediately and under no circumstance should this exceed 24 hours. The investigator will submit any updated SAE data to the sponsor within 24 hours of it being available.
- AEs will be collected from the start of Study intervention until the final follow-up contact, at the timepoints specified in the Time and Events Table (Section [8.1](#)).
- Medical occurrences that begin prior to the start of study intervention but after obtaining informed consent may be recorded on the Medical History/Current Medical Conditions section of the eCRF.

- The method of recording, evaluating and assessing causality of AEs and SAEs plus procedures for completing and transmitting SAE reports to GSK are provided in Section 12.4, Appendix 4.
- Investigators are not obligated to actively seek AEs or SAEs in former study participants. However, if the investigator learns of any SAE, including a death, at any time after a participant has been discharged from the study, and he/she considers the event reasonably related to the study intervention or study participation, the investigator must promptly notify GSK.

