- The investigator will also consult the Investigator's Brochure (IB) and/or Product Information, for marketed products, in his/her assessment.
- For each AE/SAE, the investigator **must** document in the medical notes that he/she has reviewed the AE/SAE and has provided an assessment of causality.
- There may be situations in which an SAE has occurred and the investigator has minimal information to include in the initial report to GSK. However, **it is very important that the investigator always make an assessment of causality for every event before the initial transmission of the SAE data to GSK.**
- The investigator may change his/her opinion of causality in light of follow-up information and send an SAE follow-up report with the updated causality assessment.
- The causality assessment is one of the criteria used when determining regulatory reporting requirements.

Follow-up of AE and SAE

- The investigator is obligated to perform or arrange for the conduct of supplemental measurements and/or evaluations as medically indicated or as requested by GSK to elucidate the nature and/or causality of the AE or SAE as fully as possible. This may include additional laboratory tests or investigations, histopathological examinations, or consultation with other health care professionals.
- If a participant dies during participation in the study or during a recognized follow-up period, the investigator will provide GSK with a copy of any post-mortem findings including histopathology.
- New or updated information will be recorded in the originally completed CRF.
- The investigator will submit any updated SAE data to GSK within 24 hours of receipt of the information.

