12.4.5. Reporting of SAE to GSK

SAE Reporting to GSK via Electronic Data Collection Tool

- The primary mechanism for reporting SAE to GSK will be the electronic data collection tool.
- If the electronic system is unavailable, then the site will use the paper SAE data collection tool (see next section) in order to report the event within 24 hours.
- The site will enter the SAE data into the electronic system as soon as it becomes available.
- The investigator or medically-qualified sub-investigator must show evidence within the eCRF (e.g., check review box, signature, etc.) of review and verification of the relationship of each SAE to IP/study participation (causality) within 72 hours of SAE entry into the eCRF.
- After the study is completed at a given site, the electronic data collection tool will be taken off-line to prevent the entry of new data or changes to existing data.
- If a site receives a report of a new SAE from a study participant or receives updated data on a previously reported SAE after the electronic data collection tool has been taken off-line, then the site can report this information on a paper SAE form (see next section) or to the medical monitor/SAE coordinator by telephone.
- Contacts for SAE reporting can be found in SRM.

SAE Reporting to GSK via Paper CRF

- Facsimile transmission of the SAE paper CRF is the preferred method to transmit this information to the **medical monitor or the SAE coordinator**.
- In rare circumstances and in the absence of facsimile equipment, notification by telephone is acceptable with a copy of the SAE data collection tool sent by overnight mail or courier service.
- Initial notification via telephone does not replace the need for the investigator to complete and sign the SAE CRF pages within the designated reporting time frames.
- Contacts for SAE reporting can be found in SRM.

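### Section 8.5.4 opens the paper SAE route only once an outage has passed 24 hours, which disagrees with Appendix 4 and can make a report late in a long outage

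*Protocol*

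**What the plan says.** **The deadline.** Section 8.5.1 requires every SAE to be "reported to the sponsor or designee immediately and under no circumstance should this exceed 24 hours". Section 8.5.4 says that SAEs "will be reported promptly by the investigator to the medical monitor as described in Table 4". The row of Table 4 for all SAEs gives 24 hours for both initial and follow-up reports and names the SAE data collection tool as the document. Section 12.4.4 applies the same limit to updates: "The investigator will submit any updated SAE data to GSK within 24 hours of receipt of the information".

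**The back-up route in the main body.** Below Table 4, Section 8.5.4 makes the electronic tool the primary route and then says: "If the electronic system is unavailable for greater than 24 hours, the site will use the paper SAE data collection tool". The form is faxed to the Medical Monitor, and the data are entered electronically when the system returns. The section also mentions paper or telephone reporting, but only for SAE information received after the tool has been taken off-line at the end of the study at that site.

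**The back-up route in Appendix 4.** Section 12.4.5 says: "If the electronic system is unavailable, then the site will use the paper SAE data collection tool (see next section) in order to report". The sentence closes by giving the deadline as its purpose: "in order to report the event within 24 hours". It has no waiting period. Telephone is allowed in rare circumstances when there is no fax, with the caution that "Initial notification via telephone does not replace the need for the investigator to complete and sign the SAE CRF pages" within the set time frames.

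**The concern.** Both sections cover one situation (the electronic system is down) and one tool (the paper SAE form), yet they start its use at different times. The 24-hour wait in 8.5.4 is as long as the whole reporting period, so the back-up can open after the report was due.

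What is at stake is the timeliness of SAE reports. Section 8.5.6 treats prompt notification of SAEs related to study intervention as essential to the sponsor's legal and ethical duties. The synopsis states that the trial has no data monitoring committee. For the injectable arm, Section 6.8.1 notes that both drugs may be measurable for more than a year after injection. The conflict also leaves monitors without a single standard for judging whether a report made during an outage was late.

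**Working it through.** The plan states no figure to reproduce. The check compares the two triggers with the deadline.

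**Inputs**
- Deadline: 24 hours (Section 8.5.1; Table 4 in Section 8.5.4).
- Paper trigger A: outage longer than 24 hours (Section 8.5.4).
- Paper trigger B: any unavailability (Section 12.4.5).

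**Set-up.** Let t = 0 be the moment the reporting clock starts, taken here as site awareness. Section 8.5.4 ties prompt reporting to the investigator's determination that the event meets its definition. If that is the start, measure s from there and the results below are unchanged. The deadline is t = 24 h. Let the outage start at t = s.

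- Trigger A: paper opens after t = s + 24. Time left to the deadline is under 24 − (s + 24) = −s hours.
- Trigger B: paper opens at once. Time left is 24 h if s ≤ 0, and 24 − s hours if 0 < s < 24.

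**Outage still running at hour 24**

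| Outage starts | Trigger A opens | Time left under A | Time left under B |
|---|---|---|---|
| at awareness (s = 0) | after hour 24 | none | 24 h |
| after awareness (0 < s < 24) | after hour 24 + s | none | 24 − s h |
| 2 h before (s = −2) | after hour 22 | under 2 h | 24 h |
| 12 h before (s = −12) | after hour 12 | under 12 h | 24 h |
| 24 h or more before | at awareness or directly after | about 24 h | 24 h |

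In the second row the site had s hours with a working system. Its report is late only if it was not entered in that time.

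**Outage over before hour 24.** Electronic entry is possible again and can be on time without paper. For an outage that starts at awareness, a 3-hour outage leaves 24 − 3 = 21 hours and a 20-hour outage leaves 24 − 20 = 4 hours.

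**Other routes under 8.5.4.** Its telephone option applies only after the tool is taken off-line at study completion. The section names no other route during an outage.

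**The case against.** The strongest reply is that 8.5.4 says when a site will use paper and does not forbid using it earlier. A site that faxes the form two hours into an outage breaches nothing, so all the passages can be obeyed together by following the stricter one. Section 8.5.1 also sets the overriding limit, and Sections 8.5.1 and 8.5.2 both refer the reader to Appendix 4 for transmitting SAE reports. On this view 8.5.4 is a loosely worded trigger and nothing more.

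Much of this stands. A reader might infer that 8.5.4 makes the deadline unattainable, or that it is missed in every outage. The documents do not support that. Short outages end in time for electronic entry, outages that began before awareness leave some time on paper, and a site that reads Appendix 4 will report on time. Nor does the lack of a data monitoring committee make this trigger the control on which participant protection depends. Section 7.1.1.1 requires liver stopping events to be reported to the Medical Monitor within 24 hours, and the footnote to the DTG + RPV risk table in Section 2.3.1 describes laboratory toxicity alerts and in-stream review by a safety team.

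The mismatch itself is not answered. Section 8.5.4 is the section on prompt SAE reporting, its only stated route during an outage carries the 24-hour wait, and the protocol gives no order of precedence between it and Appendix 4. The SPM, to which 8.5.4 also refers, is not among the documents. It can neither be relied on to settle the conflict nor be assumed to contain it.

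**Conclusion.** The point holds as a conflict between Sections 8.5.4 and 12.4.5, and between the 8.5.4 trigger and the 24-hour limit in 8.5.1 and Table 4. It should be corrected.

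Its reach is narrow. A late report follows when four conditions meet: the outage starts at or after awareness, it lasts past hour 24, the event was not entered before the system went down, and the site follows 8.5.4 alone. When the outage began h hours before awareness (0 < h < 24) and continues, the effect is a paper window of less than h hours in place of 24. How often either case would arise cannot be estimated, because the documents say nothing about how often or how long the system is down.

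The conclusion assumes that a site reads the stated trigger as the point at which paper begins. That is an inference from the wording, but a fair one, since 8.5.4 offers nothing else during an outage. No endpoint, analysis population, sample size or estimate is affected.

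**What to change.** In Section 8.5.4, delete the qualifier that the outage must exceed 24 hours and align the sentence with Section 12.4.5. When the electronic system is down, the site should complete the paper SAE form and fax it to the Medical Monitor in time to meet the 24-hour limit. Keep the next instruction, to enter the data electronically once the system is back, and leave the separate rule for SAEs learned of after the tool is taken off-line. Then check that the SPM gives the same trigger.

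The cost is one sentence in the protocol and one check of a manual. No data collection, dose, clinical rule or analysis changes.

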8.5.5. Disease-Related Events and/or Disease-Related Outcomes Not Qualifying as SAEs

Disease related events (DREs) or outcomes listed in the CDC Classification System for HIV-1 Infections (Section 12.8) can be serious/life threatening and will be recorded on the HIV-Associated Conditions eCRF page if they occur. However, these individual events or outcomes, as well as any sign, symptom, diagnosis, illness, and/or clinical laboratory abnormality that can be linked to any of these events or outcomes are not reported to GSK as AEs and SAEs even though such event or outcome may meet the definition of an AE or SAE. However, if either of the following conditions applies, then the event must be recorded and reported as an SAE (instead of a DRE):

- The investigator determines that the event or outcome qualifies as an SAE under part ‘other situations’ of the SAE definition (see Section 12.4.2), or
- The event is, in the investigator’s opinion, of greater intensity, frequency, or duration than expected for the individual participant, or
- The investigator considers that there is a reasonable possibility that the event was related to treatment with the investigational product, or
- Death occurring for any reason during a study, including death due to a disease-related event, will always be reported promptly.
- Lymphomas and invasive cervical carcinomas are excluded from this exemption; they must be reported as SAEs even if they are considered to be HIV-related.

If any of the above conditions is met then record the DRE on the SAE page rather than the HIV Associated Conditions eCRF page and report promptly (i.e., expedited reporting, see Section 8.5.4) to GSK.

8.5.6. Regulatory Reporting Requirements for SAEs

Prompt notification by the investigator to GSK of SAEs related to study intervention (even for non- interventional post-marketing studies) is essential so that legal obligations and ethical responsibilities towards the safety of participants and the safety of a product under clinical investigation are met.

The Sponsor has a legal responsibility to notify both the local regulatory authority and other regulatory agencies about the safety of a product under clinical investigation. GSK will comply with country specific regulatory requirements relating to safety reporting to the regulatory authority, IRB/ IEC and investigators.

Investigator safety reports are prepared for suspected unexpected serious adverse reactions according to local regulatory requirements and GSK policy and are forwarded to investigators as necessary.

An investigator who receives an investigator safety report describing a SAE(s) or other specific safety information (e.g., summary or listing of SAEs) from GSK will file it with the IB and will notify the IRB/IEC, if appropriate according to local requirements.

8.5.7. Cardiovascular and Death Events

Investigators will be required to fill out the specific CV event page of the eCRF for the following AEs and SAEs:

- Myocardial infarction/unstable angina
- Congestive heart failure
- Arrhythmias
- Valvulopathy
- Pulmonary hypertension
- Cerebrovascular events/stroke and transient ischemic attack
- Peripheral arterial thromboembolism
- Deep venous thrombosis/pulmonary embolism
- Revascularisation

This information should be recorded in the specific cardiovascular eCRF within one week of when the AE/SAE(s) are first reported. The CV CRFs are presented as queries in response to reporting of certain CV medical dictionary for regulatory activities (MedDRA) terms.

For any cardiovascular events detailed above, whether or not they are considered SAEs, and all deaths, specific Cardiovascular (CV) and Death sections of the eCRF will be required to be completed. These sections include questions regarding cardiovascular (including sudden cardiac death) and non-cardiovascular death.

The CV CRFs are presented as queries in response to reporting of certain CV MedDRA terms. The CV information should be recorded in the specific cardiovascular section of the eCRF within one week of receipt of a CV Event data query prompting its completion.

8.5.8. Death Events

The Death CRF is provided immediately after the occurrence or outcome of death is reported. Initial and follow-up reports regarding death must be completed within one week of when the death is reported.

In addition, all deaths will require a specific death data collection tool to be completed. The death data collection tool includes questions regarding cardiovascular (including sudden cardiac death) and noncardiovascular death.

8.6. Toxicity Management

Adverse events that occur during the trial should be evaluated by the Investigator and graded according to the Division of AIDS (DAIDS) toxicity scales (See Section 12.3. “Division of AIDS Table for Grading the Severity of Adult and Pediatric Adverse Events”). Additional information regarding detecting, documenting and reporting AEs and SAEs are available in Section 8.5 and Section 12.4.

8.6.1. Treatment Interruption Due to an Adverse Event

IP may be interrupted at the discretion of the investigator and according to the severity of the AE. If one or more ART medication is held due to toxicity or AEs, all ART medications should be held to reduce the risk of development of resistance taking into account the length of the planned interruptions and the PK half-life of each ART of the regimen, in order to minimize the risk of development of resistance.

No toxicity-related dose reductions of IP will be allowed. IP should be restarted as soon as medically appropriate; in general, for oral dosing, this should be no longer than 14 days after discontinuation (unless Grade 3 or 4 toxicities persist). Any interruption in therapy during the Maintenance Phase, oral dosing, of greater than 7 consecutive days must be discussed with and agreed by the Medical Monitor prior to resumption of therapy. The Medical Monitor must be contacted upon becoming aware of resumption in therapy, if therapy was resumed without prior approval (Section 6.8). **IM dosing is expected to occur during the month in which the participant’s projected visit falls (as according to the first injection visit). An additional (+ or -) 7 day window, from the projected visit date, is stipulated for IM dosing.** Any interruption outside of this guidance MUST be discussed with the Medical Monitor prior to reinitiating IM IP (see Section 6.8.1).

Guidance is provided below on general participant management and IP interruptions based on the severity of the AE. Information regarding permitted substitutions \ is provided in Section 6.7.1.1. All changes in the IP regimen must be accurately recorded in the participant’s eCRF.

Note: For participants receiving an ABC-containing product as part of the background regimen during the Long-Term Follow-Up (LTFU) Phase, in the event of a discontinuation of ABC for any reason, re-initiation of this drug should be undertaken with caution. The investigator should obtain a complete history of the events surrounding the discontinuation of the ABC-containing product, evaluate for the possibility of a clinically suspected HSR, and initiate participant management as outlined in the Local Country Prescribing Information, regardless of a participant’s human leukocyte antigen (*HLA*)-*B*5701* status. Screening for the presence of *HLA*-*B*5701* is recommended prior to reinitiating treatment with ABC-containing products in participants of unknown *HLA*-*B*5701* status who have previously tolerated ABC but is not required to confirm study eligibility.

